Preliminary and Primary Data Analyses. As the proposed study is a small-sample pilot study, our primary focus will be on examining feasibility, acceptability, and direction of effects. Additionally, all randomized participants will be used in an intent-to-treat analysis. We will use chi-square and t-tests to evaluate any differences between the two conditions at baseline on demographic and other relevant variables, such as initial symptom severity, comorbid depression, or patient adherence to ERP homework. If significant differences exist, we will covary for these variables in our analyses (though we do not anticipate significant group differences at baseline, as urn randomization tends to result in balanced samples.)

Aim 1: Establish feasibility and acceptability of research procedures and clinical intervention.

Hypothesis: Patients with OCD will tolerate this combined ERP + tDCS treatment and will find it acceptable, as determined by rates of retention, treatment completion, and patient report. For Aim 1, we will use chi-square or t-test to compare treatment conditions on rates of retention, session attendance, homework and treatment completion, and patient satisfaction on the CSQ-8.

Aim 2: Gather evidence on preliminary efficacy of tDCS over rIFG as an adjunct to ERP for OCD.

Hypothesis: Patients in the group receiving ERP + active tDCS will show greater reduction in symptom severity over 10 sessions of the combined treatment than those receiving ERP + sham tDCS. For Aim 2, we will use repeated-measures ANOVA with a between-group factor (condition) to evaluate differences in Y-BOCS severity between groups across assessment timepoints. Since this is a small pilot study (N=32), we will also examine group means and direction of effects across all timepoints, not relying solely on statistical approaches which may be underpowered to detect a significant effect.

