Aim 3: Characterize the relationship between measures of inhibitory control and outcome of the combined intervention. Hypotheses: a) Response inhibition, as measured by the SST, will improve more after ERP plus active vs sham tDCS; b) Improvement in OCD severity will correspond to improved inhibitory control on the SST; and c) Patients receiving ERP plus active tDCS will report less difficulty inhibiting compulsions during ERP exercises than those receiving ERP plus sham tDCS. To test our hypotheses for Aim 3, we will: a) use independent measures t-tests to compare change in SSRT from pre- to post-treatment between conditions, and from pre-treatment to follow-up; b) compute a correlation between percent change in Y-BOCS score and percent change in SSRT from baseline to post-treatment, and from baseline to 1-month follow-up, c) use an independent measures t-test to compare self-reported mean difficulty inhibiting compulsions (VAS) during ERP across stimulation conditions.

Revised Data Analysis Plan:

Preliminary and Primary Data Analyses. Given that this study resulted in a smaller than anticipated final sample size, we created a revised analysis plan, appropriate for the smaller sample. Consistent with the original plan for this pilot study, our primary focus will be on examining feasibility, acceptability, and direction of effects. Additionally, all randomized participants will be used in an intent-to-treat analysis. Analyses will focus on descriptive statistics (e.g., means or proportions) with between-group effect sizes calculated, as appropriate.

Aim 1: Establish feasibility and acceptability of research procedures and clinical intervention.

Hypothesis: Patients with OCD will tolerate this combined ERP + tDCS treatment and will find it acceptable, as determined by rates of retention, treatment completion, and patient report. Our primary feasibility outcome of interest is rates of session completion. Our primary acceptability outcome is patient-reported client satisfaction.

Aim 2: Gather evidence on preliminary efficacy of tDCS over rIFG as an adjunct to ERP for OCD.

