There are relatively few risks involved in the proposed study. Potential risks to all subjects include: (1) Coercion. Subjects may feel coerced to participate, (2) Breach of confidentiality or loss of privacy. In the course of this study we will collect sensitive information which, if released, may cause shame, embarrassment, or distress; (3) Distress due to assessment procedures. During the assessments we will ask participants about their thoughts, feelings, behaviors, and symptoms. It is possible that asking participants about this information may increase distress or discomfort. (4) Risks due to tDCS. There is some inherent risk with tDCS, mainly risk of skin irritation and, as in a small number of case reports, local skin burns where the electrodes are attached. Such cases have typically been seen only after repeated daily stimulation to the same region (Palm, 2008), or after unintentional abrasion of the skin with alcohol swabs prior to stimulation (Loo, 2011). Though a possible risk, skin burns are rare. In a recent review of clinical research with tDCS, Brunoni and colleagues (2011) noted that “tDCS has been tested in thousands of subjects world-wide with no evidence of toxic effects to date.” In addition, we are aware of reports of a small percentage of patients developing temporary hypomania during the course of a daily tDCS protocol for depression targeting the dorsolateral prefrontal cortex. It is unclear whether this is a risk for tDCS targeting rIFG or with the electrode montage used in this study. The most common side effects include mild local sensations at the electrode sites, including tingling or itching, and moderate fatigue, and headache (Brunoni, 2011; Poreisz, 2007). In general, these effects have paralleled those of sham stimulation. In research experience totaling 567 tDCS sessions, no participants requested tDCS be stopped or required any medical intervention during or after stimulation. Notably, adverse effects did not differ between healthy individuals and patients (Poreisz, 2007). Safety testing of tDCS has found high tolerability and no reports of discomfort by participants when stimulating for 20 minutes at either 1 or 2mA for 20 minutes (Iyer, 2005). (5) Distress due to treatment procedures. Treatment of OCD with ERP involves patients facing situations which make them anxious, both directly and in their imaginations.

D. Protection of the Subject (include measures to minimize potential risks and to ensure confidentiality)

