future research studies. (2) To minimize the risk of distress arising from the assessment procedure, study staff that has been adequately trained in the assessment battery will complete all assessments, and [the PIs] will supervise all assessors. (3) To minimize risks due to tDCS, all participants will be carefully screened prior to tDCS for contraindications to tDCS. Moreover, we will obtain a release to gather information from participants' current medical providers for screening purposes and ongoing clinical record keeping. All tDCS will be administered by a trained member of the research staff under the supervision of a credentialed physician (Dr. [Name] or covering physician). Use of an electrically isolated power source (i.e., battery-powered DC stimulation device) also protects against delivery of more intense currents than intended. Participants will be closely observed for signs of skin burns, discomfort, or other stress. Participants will be closely monitored to ensure the electrode sponges stay moist with saline in order to help prevent burns by improving electrode-to-skin contact. Participants will have the option of discontinuing the study at any time and will be explicitly instructed to inform the experimenters immediately if they experience any discomfort. The experimenter will inform the supervising physician about any participant who has significant skin discomfort or a skin lesion after current delivery. If there is any doubt about the mental or physical status of an individual after testing, the PI or other supervising physician will evaluate the participants and make a recommendation for follow-up care, if required. Telephone or in-person follow-up will be arranged as needed and will not be considered a protocol deviation. Adverse effects will be monitored regularly using the SAFTEE-SI. This measure includes symptoms of hypomania, including feeling hyper, unable to sit still, changes in appetite, and sleep disturbance, as well as a number of frequently reported side effects in clinical trials. Any participant judged on clinical grounds to have suffered adverse effects will thus be evaluated and treated as necessary and withdrawn from the study, if necessary. For each SAFTEE item, participants are asked to report how bothersome each symptom on the form has been for him/her in the past week, with response options "None," "Mild," "Moderate," or "Severe." Additionally, a single item inquires about how much all reported side-effects have bothered the participant or interfered with daily activities (response options: "No side effects," "Mildly," "Moderately," or "Markedly"). The SAFTEE-SI will be administered at baseline, once per week during the 5.5 week protocol, at post-treatment, and at 1 month follow-up. At each administration, the evaluator will note items rated more bothersome than during the previous administration and will inquire further about each such item. The therapist or evaluator will also inquire in an open-ended fashion about any other adverse effects experienced which are not listed on the SAFTEE-SI and will document the nature and tolerability of any additional side-effects reported. For any item rated "severe," or if the participant reports that side effects are interfering with daily activities "markedly," the therapist or evaluator will notify Dr. [Name] MD (PI) (or covering physician) immediately. Dr. [Name] (or covering physician) will provide further evaluation as medically necessary and we will take appropriate safety measures such as study withdrawal and/or referral to higher level of clinical care, if necessary. Any item rated as "moderate" or "moderately" interfering will be reported to Dr. [Name] by the therapist or evaluator within 24 hours. All other reported side-effects endorsed on the SAFTEE-SI will be discussed with Dr. [Name] during weekly meetings of study staff. Follow-up or further evaluation will occur as medically necessary. (4) To minimize the risk of distress due to treatment procedures, we have selected a treatment which has been shown to be efficacious in reducing OCD symptoms. While this treatment involves clients placing themselves in situations which provoke anxiety, this is necessary and effective for clinical improvement and generally represents no more distress than is experienced in daily living for these individuals. Participants will be informed that they will be encouraged to

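### Does Aim 1 need a named side-effect summary before the trial can say that patients tolerated the treatment?

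*Combined protocol and SAP*

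**What the plan says.** The Aim 1 hypothesis, the same in Specific Aims (II.A) and in both versions of Data Analysis (II.C.4), is that patients "will tolerate this combined ERP + tDCS treatment and will find it acceptable, as determined by rates of retention, treatment completion, and patient report".

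The Original Data Analysis Plan compares the arms on "rates of retention, session attendance, homework and treatment completion, and patient satisfaction on the CSQ-8". The Revised Data Analysis Plan, written once the sample was known to be smaller than intended, keeps the hypothesis and names two lead measures: "Our primary feasibility outcome of interest is rates of session completion" and "Our primary acceptability outcome is patient-reported client satisfaction". It says in general that analyses will be descriptive, using averages and proportions with between-group effect sizes where suitable. Neither version mentions the SAFTEE-SI or adverse events.

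Side effects are dealt with elsewhere. Monitoring Assessments (II.C.3) describes the modified SAFTEE-SI as a 55-item self-report form. Section III.D.1 says of it: "This measure includes symptoms of hypomania, including feeling hyper, unable to sit still, changes in appetite, and sleep disturbance". It adds that "a single item inquires about how much all reported side-effects have bothered the participant or interfered with daily activities". Section III.C mentions temporary hypomania in a daily depression protocol aimed at a different cortical target and comments: "It is unclear whether this is a risk for tDCS targeting rIFG or with the electrode montage used in this study".

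**The concern.** Tolerability is a claim about side effects, yet the measures that the plans list under Aim 1 are attendance, completion, homework and satisfaction. Under III.D.1, a participant judged to have adverse effects "will thus be evaluated and treated as necessary and withdrawn from the study, if necessary", so someone can have troublesome side effects and still complete every session. Retention would not register that person. In the other direction, some of the listed withdrawal reasons, such as physical illness or starting another treatment, need have nothing to do with tolerability.

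The hypomania remark sharpens the worry. The protocol calls the risk unclear, collects relevant symptoms in a sham-controlled design, and names no comparison by arm. Feasibility and acceptability are the stated primary focus of the pilot. If the plan were followed to the letter and no further, the report could say that patients tolerated the treatment and show no side-effect count.

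**Working it through.** The documents give no tolerability rate or threshold, so there is no figure to reproduce. The check has four steps.

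**1. Are the data collected in both arms?** Monitoring Assessments lists baseline, sessions 1, 3, 5, 7 and 9, post-treatment and one month: 1 + 5 + 1 + 1 = 8 administrations, of which 7 follow baseline. Material Inducements (II.D) lists the same eight assessment points. Nothing restricts the form to one arm.

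**2. Do the plans exclude the SAFTEE-SI?** Set three statements side by side. Aim 1 judges tolerability partly by patient report. Monitoring Assessments calls the SAFTEE-SI a self-report measure. The revised plan calls for descriptive summaries. Together they permit a side-effect table by arm. Naming a primary feasibility outcome and a primary acceptability outcome does not close the list of what is reported.

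**3. Do the named measures ignore side effects?** Only in part. Take 32 / 2 = 16 per arm (equal arms are an assumption; the allocation ratio is not stated). One participant with a severe item who stays moves retention by 0 points, and would move a count of severe ratings by 1/16 = 6.25 points. So retention alone can miss that participant. But satisfaction may differ for that person. A severe rating also goes to the physician at once, with withdrawal possible, so it is not independent of retention. Of the seven withdrawal reasons, one is by definition a reaction to tDCS. Clinical deterioration, the investigators' decision, the participant's decision and even missed visits can also reflect poor tolerance of the combined treatment, which is what Aim 1 is about.

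**4. Would naming the table make the answer more precise?** For 0 affected out of n, the exact two-sided 95% upper limit is 1 − 0.025^(1/n). The final sample size is not given, so 12 and 8 per arm are assumptions.

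| n per arm | Upper limit for 0/n |
|---|---|
| 16 | 20.6% |
| 12 | 26.5% |
| 8 | 36.9% |

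These limits depend on n alone and are the same whether or not the plan names the table. If the true rate of some event were 5% (assumed), the chance of seeing at least one case is 1 − 0.95^n: 56% at n = 16 and 34% at n = 8. The hypomania question could not be settled here under any wording.

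**The case for a change.** The strongest case for a change is that permission is not a plan. Satisfaction is the only patient-reported outcome that the revised plan names for Aim 1, so a reader may fairly take patient report to mean the CSQ-8. With 55 items and 7 administrations after baseline, there are 55 × 7 = 385 ratings per completer, and no threshold or time window is set, so a favourable cut could be chosen after seeing the data. Physician alerts and board review manage individual cases and do not produce a result. A sentence of text would settle the matter at almost no cost.

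Part of this stands. The SAFTEE-SI is not named, and a named summary would be tidier. But the form contains one overall bother and interference item, so a natural summary is available without searching 385 ratings. Anything specified now would also follow knowledge of the final sample size, which limits what pre-specification could still add.

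The hypomania argument carries less weight than it seems to. The remark is a risk disclosure and no aim poses it as a question. The reports concerned daily stimulation of another region in depression, whereas this trial schedules two sessions a week and excludes lifetime bipolar disorder. The symptoms listed are non-specific in patients undergoing exposure therapy. Section III.C gives skin irritation as the main tDCS risk, so a summary built around hypomania would miss the effect that the protocol itself puts first.

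**Conclusion.** No change follows. This is missing detail of a kind that analysts fill sensibly: no stated rule gives a wrong result, the instrument fits the plan's own patient-report criterion, and the descriptive approach accommodates a side-effect table by arm. Withdrawal reasons are documented, adverse event forms are completed, and the data safety monitoring board can review side effects (III.D.3), so the information exists and is looked at during the trial.

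The effect on the Y-BOCS, SSRT, session-completion and satisfaction results is nil. The precision of any side-effect rate is set by the sample size and would not improve with different wording. The conclusion rests on reading patient report to include a self-report side-effect form, and on the ordinary expectation that a sham-controlled pilot reports side effects by arm. If the trial report claimed tolerability and showed no such figures, that would be a fault in the report, since this plan leaves room for them.

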To monitor for symptom change, short assessments will be given at baseline, and approximate weekly (see Table 1) during treatment (for clinical symptoms monitoring), post-treatment, and 1-month after treatment, using the Y-BOCS^{43, 44}; BDI-II⁴⁵ (see "Screening," above); and the Beck Anxiety Inventory (BAI),⁴⁶ to assess general anxiety symptoms. The

Patient Ex/RP Adherence Scale (PEAS)⁴⁷ will be used at each ERP session to assess adherence to ERP homework, since adherence relates to treatment outcome.⁴⁸ Patients will also complete the 8-item Client Satisfaction Questionnaire (CSQ-8)⁴⁹ at post-treatment and 1-month follow-up to assess satisfaction with the intervention. A modified version of the Systematic Assessment for Treatment Emergent Events-Specific Inquiry (SAFTEE-SI) will be administered assess for emergent side-effects. This is a self-report measure which inquires about the presence and severity of 55 of the most commonly reported side effects in clinical trials, as well as how much reported side effects bother patients or interfere with daily activities. The SAFTEE-SI will be administered at baseline, at sessions 1, 3, 5, 7, and 9, at post-treatment, and at 1 month follow-up. At each administration, the evaluator or therapist will note items rated more bothersome than during the previous administration. The therapist or evaluator will inquire further about each such item, including asking for a description of the side effect, when it occurs, how much it interfered, and what the participant attributes the symptom to. The therapist or evaluator will also inquire in an open-ended fashion about any other adverse effects experienced which are not listed on the SAFTEE-SI and will document the nature and tolerability of any additional side-effects reported. For any item rated "severe," or if the participant reports that side effects are interfering with daily activities "markedly," the therapist or evaluator will notify Dr. [Name] MD (PI) (or covering physician) immediately and Dr. [Name] (or covering physician) will provide further evaluation as medically necessary. Any item rated as "moderate" or

Date most recently revised (02/16/18)

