Hypothesis: Patients in the group receiving ERP + active tDCS will show greater reduction in symptom severity over 10 sessions of the combined treatment than those receiving ERP + sham tDCS. For Aim 2, we will examine group means on the Y-BOCS and direction of effects at post-treatment, and 1-month follow-up, not relying on statistical approaches which will be underpowered to detect an effect. The Y-BOCS is our primary clinical outcome.

Aim 3: Characterize the relationship between measures of inhibitory control and outcome of the combined intervention. Hypotheses: a) Response inhibition, as measured by the SST, will improve more after ERP plus active vs sham tDCS; b) Improvement in OCD severity will correspond to improved inhibitory control on the SST; and c) Patients receiving ERP plus active tDCS will report less difficulty inhibiting compulsions during ERP exercises than those receiving ERP plus sham tDCS. We regard aim 3 and related hypotheses to be largely exploratory. To investigate our hypotheses for Aim 3, we will: a) calculate mean change in SSRT from pre- to post-treatment, and from pre-treatment to follow-up for both conditions, and between groups effect size; b) compute a correlation between percent change in Y-BOCS score and percent change in SSRT from baseline to post-treatment, and from baseline to 1-month follow-up, c) calculate self-reported mean difficulty inhibiting compulsions (VAS) during ERP and direction of effects across stimulation conditions.

D. Material Inducements

Compensation for participation in assessments will be offered as part of this study. No compensation will be offered for participation in ERP sessions. Participants will receive a payment of \$25 for completing the screening assessment. Participants will participate in a total of 8 additional assessments during the study (baseline, sessions 1, 3, 5, 7, 9, post-treatment, and 1 month follow-up); they will receive payment for completion of each of these assessments (\$30 for the baseline assessment, \$10 for each mid-treatment assessments, \$40 for the baseline assessment, and \$40 for the post-treatment assessment) for maximum compensation of \$185 for completing the screening and all assessments. Participants will have the option to receive payment by check in the mail or Stop & Shop gift card after each assessment.

E. Training of Research Personnel

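### Revised Aim 2 hypothesises a greater reduction in Y-BOCS but does not say how baseline Y-BOCS enters the group comparison

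*Combined protocol and SAP*

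**What the plan says.** The Aim 2 hypothesis in the Revised Data Analysis Plan (section II.C.4) is that patients on active stimulation "will show greater reduction in symptom severity over 10 sessions of the combined treatment" than those on sham. The readout is that "we will examine group means on the Y-BOCS and direction of effects at post-treatment, and 1-month follow-up", with no reliance on statistical testing. The plan adds: "The Y-BOCS is our primary clinical outcome". The general paragraph of the revised plan promises descriptive statistics "with between-group effect sizes calculated, as appropriate", without saying on which quantity.

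Baseline Y-BOCS is available. The Monitoring Assessments section says "To monitor for symptom change, short assessments will be given at baseline" and names the Y-BOCS among them. Table 1 marks the Y-BOCS at both screening and baseline. Under Aim 3b the same revised plan does use Y-BOCS change: it will "compute a correlation between percent change in Y-BOCS score and percent change in SSRT from baseline to post-treatment". Aim 3a likewise specifies change in SSRT from pre-treatment.

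The Original Data Analysis Plan brought baseline in through a repeated-measures ANOVA and a rule to covary for significant baseline differences. The revised plan restates neither.

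**The concern.** A reduction is a statement about change from a starting level; a mean at follow-up is not. The exploratory Aim 3 has a defined contrast with baseline, while the primary clinical outcome has none. The plan does not exclude baseline. It is silent, which leaves at least three comparisons open: raw follow-up means, change from baseline, and follow-up means adjusted for baseline.

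In a large trial the three would usually agree in sign. In a small one they need not. Raw follow-up means are unbiased over repeated randomisation, but in the one trial actually run they carry part of any chance baseline gap into the result. They also use the data less efficiently when baseline and outcome are moderately correlated. Because Aim 2 reports a direction rather than a test, an unspecified contrast leaves the main statement of Aim 2 unspecified.

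**Working it through.** The documents give no SD, effect size or power calculation, so there is no figure of the plan's own to reproduce. What follows illustrates the size of the problem.

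**Inputs.** The planned total is 32, so 16 per arm if split equally (the allocation ratio is not stated). The revised plan says the final sample was smaller and gives no number; 10 and 8 per arm are assumed, and 16 serves as an upper bound. Also assumed: equal SDs at both visits, simple randomisation, a true benefit of 0.4 SD, and a baseline-outcome correlation r of 0.3 to 0.7.

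**Chance baseline gap.** The SE of a difference in means, in SD units, is √(2/n): 0.354, 0.447 and 0.500 at 16, 10 and 8 per arm. The probability of a gap above 0.5 SD in either direction is 2[1 − Φ(0.5/SE)] = 16%, 26% and 32%.

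**Do raw means and change agree in sign?** The variances of the two group differences are 2/n and (2/n)·2(1 − r), with covariance (2/n)(1 − r), so their correlation is √((1 − r)/2).
- With no true effect, the chance of opposite signs is arccos(√((1 − r)/2))/π, whatever n. That is 30%, 33% and 37% at r = 0.3, 0.5 and 0.7.
- With a true effect of 0.4 SD, it is P(raw wrong) + P(change wrong) − 2·P(both wrong) from the bivariate normal. That is 15% to 17% at 16 per arm, 21% to 22% at 10, and 22% to 24% at 8, over r = 0.3 to 0.7.

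**How often does each contrast favour the wrong arm?** Raw: Φ(−0.4/SE). Change: Φ(−0.4/(SE·√(2(1 − r)))). Adjusted: 400,000 simulated trials per cell, with the pooled within-arm slope estimated in each.

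| Contrast | 16 per arm | 10 per arm | 8 per arm |
|---|---|---|---|
| Raw follow-up means, any r | 12.9% | 18.6% | 21.2% |
| Change, r = 0.3 | 16.9% | 22.5% | 24.9% |
| Change, r = 0.6 | 10.3% | 15.9% | 18.6% |
| Adjusted, r = 0.3 | 12.2% | 18.1% | 21.0% |
| Adjusted, r = 0.5 | 10.0% | 15.8% | 18.7% |
| Adjusted, r = 0.6 | 8.3% | 13.9% | 16.8% |
| Adjusted, r = 0.7 | 6.0% | 11.2% | 14.1% |

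At r = 0.5 change and raw means are equally precise, because 2(1 − 0.5) = 1. At 5 per arm and r = 0.3 adjustment gains nothing (26.7% against 26.4% raw).

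**Given a baseline gap.** With equal SDs, a gap g moves the raw follow-up difference by r·g on average. At r = 0.6 and g = 0.5 SD that is 0.30 SD, three quarters of the assumed effect. If the active arm starts more than 0.5 SD worse (chance 8%, 13%, 16%), raw means point the wrong way in 49%, 53% and 55% of trials at r = 0.6, against 9%, 15% and 18% adjusted. At r = 0.3 the figures are 27%, 34% and 36% against 13%, 19% and 22%. A gap in the other direction shifts raw means by the same amount in favour of active stimulation.

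**Precision.** The 95% half-width is t(0.975, 2n − 2)·√(2/n) raw and t(0.975, 2n − 3)·√((2/n)(1 − r²)(1 + 1/(2n − 4))) adjusted. Raw gives 0.72, 0.94 and 1.07 SD. Adjusted gives 0.70, 0.93 and 1.07 at r = 0.3, and 0.59, 0.78 and 0.90 at r = 0.6.

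**The case against.** The strongest reply is that this is a descriptive pilot. No test or go/no-go rule hangs on Aim 2, and the natural reading of an effect's direction, directly after a hypothesis of reduction, is the direction of change. On that view one clarifying sentence is enough, and a model moves back towards what the revision set aside. The figures can also be called generous: 16 per arm was not reached, the most striking rates need both r = 0.6 and an unlucky gap, and the unconditional gain at 8 per arm and r = 0.3 is negligible (21.2% to 21.0%). The original plan also states that "urn randomization tends to result in balanced samples"; if Y-BOCS was a balancing variable, the imbalance rates above are too high.

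Much of this stands as a limit on size. The benefit of adjustment may be small, and the documents name no balancing variables. The gap itself remains. Reading Aim 2 as change is plausible but not written, and it still leaves change and adjusted difference open; at r = 0.3 unadjusted change does worse than raw means. The absence of a test makes the point matter more, since the sign and size of the difference are then all that is reported. A covariate-adjusted mean difference with an interval is still a descriptive estimate.

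**Conclusion.** The concern holds. The revised plan does not define the between-group contrast on its primary clinical outcome, and the readout it names does not match its hypothesis. Under the stated assumptions the choice between raw means and change alone reverses the reported direction in about 15% to 24% of trials at 16 down to 8 per arm. Baseline adjustment lowers the wrong-direction rate by about 4 to 5 percentage points at r = 0.6 (12.9% to 8.3%, 18.6% to 13.9%, 21.2% to 16.8%) and by less than 1 point at r = 0.3.

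These sizes rest on an unknown final sample size, an unknown correlation (which the entry cut-off of Y-BOCS ≥ 16 may lower), an assumed effect of 0.4 SD and simple randomisation. The specification gap rests on the text alone. It should be corrected, but it does not invalidate the trial.

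**What to change.** In the revised Aim 2, state that the active-minus-sham Y-BOCS difference at post-treatment and at 1 month is estimated from a linear model that always includes baseline Y-BOCS as a covariate, and is reported with a 95% confidence interval and no significance test. Beside it, show by arm the raw baseline means, the follow-up means and the mean change, so that both the hypothesised reduction and any baseline gap are visible. Name the visit that counts as baseline, since Table 1 has the Y-BOCS at screening and at baseline. Because the revision was written once the sample was known to be short, also record whether Y-BOCS results by arm had been seen when the contrast was fixed.

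The cost is wording, on data already in the assessment schedule, plus one degree of freedom per model. If the correlation is about 0.3 or the arms are very small, precision improves little or not at all; the gain is then only that the contrast is fixed and the baseline is shown.
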